**SmartSleep** offers an alternative to the dilemma of risking the adverse effects of chronic sleep restriction and low sleep quality in spaceflight, versus risking the adverse effects of medications on sleep and waking in ever-longer duration spaceflight. If increased amounts of slow-wave activity in sleep via SmartSleep can translate to cognitive performance benefits and/or sleep quality benefits, even during periods of chronically restricted sleep time to 5h/night, it will offer a significant advantage over the sleep medication alternative. If this is the case, it will also be essential to determine whether the enhanced slow-wave activity during sleep provided by SmartSleep will increase sleep inertia and thereby impair cognitive performance immediately following an emergent awakening. It is therefore imperative that the safety of increasing slow-wave activity be demonstrated to benefit subsequent waking cognitive performance while not exacerbating sleep-inertia performance deficits at emergent awakening. Operational safety needs to be demonstrated before the use of SmartSleep in the space program. Finally, to the best of our knowledge, a non-pharmacological slow-wave enhancing technology has not been tested in a chronic sleep restriction paradigm, despite the high prevalence of chronic sleep loss in astronauts and in the general population.

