## SPECIFIC AIMS

The overarching goal of this project is to mitigate the effects of chronic sleep loss by optimizing the SmartSleep technology and demonstrating its safety at the same time. It has the following Specific Aims:

**Specific Aim 1:** Determine whether slow-wave sleep can be enhanced via closed-loop auditory stimulation of EEG slow waves in healthy adult subjects using SmartSleep Headband technology, when sleep is restricted in duration to 5h per night over 4 consecutive nights.

Hypothesis 1: Slow wave sleep will be enhanced via closed-loop auditory stimulation of EEG slow waves relative to sham stimulation, when sleep is restricted in duration to 5h per night over 4 consecutive nights.

**Specific Aim 2:** Determine whether post-sleep cognitive performance functions sensitive to sleep restriction can be enhanced when SmartSleep closed-loop auditory stimulation is used on sleep-restricted nights relative to a sham SmartSleep control condition. Hypothesis 2: Daytime cognitive performance will be higher after closed-loop auditory stimulation of EEG slow waves relative to sham stimulation, when sleep is restricted in duration to 5h per night over 4 consecutive nights.

**Specific Aim 3:** Identify the acoustic stimulation modality with maximal benefits for slow-wave enhancement and daytime cognitive performance, when sleep is restricted in duration to 5h per night over 4 consecutive nights. Hypothesis 3: One of the three acoustic stimulation modalities enhances EEG slow waves significantly better than the other two modalities, and is also associated with enhanced cognitive performance during the daytime, when sleep is restricted in duration to 5h per night over 4 consecutive nights.

**Specific Aim 4:** Investigate systematic effects of consecutive nights of sleep restriction on slow-wave enhancement and daytime cognitive performance. Hypothesis 4: With increasing homoeostatic sleep drive induced by consecutive nights of sleep restriction, the observed slow-wave enhancement will mitigate some of the effects of chronic sleep loss on daytime cognitive performance.

**Specific Aim 5:** Assess any potential adverse effects of SmartSleep utilization during sleep restriction, especially related to sleep inertia after emergent awakening. Hypothesis 5: Cognitive functioning after emergent awakenings in the acoustic stimulation conditions will be non-inferior relative to sham stimulation based on a non-inferiority margin of 2 lapses on the PVT-B.

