## **STATISTICAL APPROACH**

We conducted a randomized, double-blind, cross-over laboratory study on the effects of the slow-wave enhancing smart sleep technology on cognitive performance during 4 consecutive nights of sleep restriction (5h time in bed). We compared the four auditory stimulation modalities (continuous fixed interval, block, in-phase adjustable, and sham) relative to their slow-wave and performance enhancing properties. Each subject was exposed to all 4 modalities (within-subject study design). We used a balanced orthogonal Latin Square design (i.e., each stimulus modality will appear in each of the 4 sleep restriction nights exactly once, and each modality will be preceded by each other modality exactly once).

Cognitive test data were standardized to baseline performance. We used linear mixed effect models (in SAS version 9.4, SAS Institute, Cary, NC) with random subject intercept to account for the clustered nature of the data. The model included factors for stimulus modality (4 levels), sleep restriction night (4 levels), and their interaction. We were both interested in the main effects (modality and sleep restriction) and their interaction, but acknowledge the limited power for detecting a significant interaction. If the type-III fixed effect estimate indicates a significant difference between groups, we compared them in post-hoc tests. The primary outcome was the number of lapses (errors of commission; response times >355 ms) on the brief Psychomotor Vigilance Test (PVT-B) after emergent awakenings and during the day. Performance on the Digit Symbol Substitution (DSST), Descending Subtraction Task (DST), and spaceflight relevant task (ROBoT) were treated as secondary outcomes. The other cognitive tests (Cognition, Spatial Cognition, tasks with operational relevance for spaceflight) were treated as tertiary outcomes. Statistical tests for secondary and tertiary outcomes were adjusted with the false discovery rate method (Curran-Everet, 2000).

For the power calculations (Figure 4), we assumed a correlation between measurements of 0.8, and varied the standard deviation of the difference between modalities/sleep restriction nights from 0.8 to 1. We expect to have >80% power to find a medium effect size of 0.5 statistically significantly different for standard deviations <0.9.

[figure not shown]

Figure 4: Power calculations

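### Hypothesis 5 claims non-inferiority within 2 PVT-B lapses, but no described analysis tests that margin; and no alpha or adjustment is stated for the pairwise daytime PVT-B tests

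*Combined protocol and SAP*

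**What the plan says.** Hypothesis 5 (SPECIFIC AIMS) is a non-inferiority claim: each acoustic condition against sham, after emergent awakening, with a margin of 2 lapses on the PVT-B. The BACKGROUND section gives the purpose: stimulation should be shown to "benefit subsequent waking cognitive performance while not exacerbating sleep-inertia performance deficits at emergent awakening". Hypothesis 2 is the daytime efficacy claim: "Daytime cognitive performance will be higher after closed-loop auditory stimulation of EEG slow waves relative to sham stimulation".

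The STATISTICAL APPROACH section makes PVT-B lapses the primary outcome "after emergent awakenings and during the day". It describes one analysis: a linear mixed model with a random subject intercept and factors for modality, night and their interaction. Then: "If the type-III fixed effect estimate indicates a significant difference between groups, we compared them in post-hoc tests". No post-hoc method or significance level is named there or elsewhere. On scale it says: "Cognitive test data were standardized to baseline performance". On multiplicity it says: "Statistical tests for secondary and tertiary outcomes were adjusted with the false discovery rate method". Nothing comparable is said for the primary outcome.

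**The concern.** **Main point.** A type-III F test asks whether the four condition means differ at all. It cannot show that a modality is no more than 2 lapses worse than sham, and the difference tests behind it do not refer to the margin either. Following the section as written leaves the safety hypothesis untested. In a 12-subject study a non-significant F could then be taken as reassurance about sleep inertia when the data do not exclude 2 extra lapses. The margin is also in raw lapses, while the data are described as standardized.

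**Secondary point.** For daytime PVT-B, the pairwise contrasts tell a reader which modality differs from sham or from another. An F-test gate protects the set of pairs when all four conditions are equal. Once one modality truly differs, the gate tends to open and the remaining null pairs are tested as well. If those tests are each at 5%, the error over the set exceeds 5%.

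**Working it through.** **1. Hypothesis 5**

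Inputs from the documents: n = 12, each subject under all four conditions (STUDY DESIGN); margin 2 lapses (SPECIFIC AIMS). Assumed, because not given: SD of the stim-minus-sham lapse difference 2, 3 or 4; two-sided 5% F test; normal errors; complete data; one value per subject-night.

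- Degrees of freedom: 12 × 4 = 48 values. Subjects, nights and modalities use 12 + 3 + 3 = 18, leaving 30. With the interaction, the Figure 2 design has rank 27, leaving 21.
- Let one modality truly add 2 lapses and the others none. The grand mean is 0.5 and the squared deviations sum to 1.5² + 3 × 0.5² = 3. The residual variance is SD²/2, so the noncentrality is 12 × 3 / (SD²/2) = 72/SD², or 18, 8 and 4.5.
- The critical F(3,30) is 2.922. The F test is non-significant in 7%, 41% and 65% (with 21 df: 9%, 44% and 66%).
- A confidence-limit rule passes a modality when difference + 2.042 × SD/√12 is below 2. At a true difference of 2 it passes 2.5% of the time, whatever the SD.
- At a true difference of 0 the noncentrality is 2√12/SD = 3.46, 2.31 and 1.73. Power per modality is 92%, 61% and 39%. With the Dunnett value 2.474 it is 83%, 45% and 25%.
- With all three modalities at the margin, the chance of at least one false non-inferiority claim is 6.2% with unadjusted limits and 2.5% with Dunnett limits.

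**2. Daytime pairs**

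The plan's own figure comes first. It states "we assumed a correlation between measurements of 0.8" and "We expect to have >80% power to find a medium effect size of 0.5 statistically significantly different for standard deviations <0.9". Reading the SD as that of a single measurement, SD of the difference = SD × √(2 × (1 − 0.8)) = 0.632 × SD. An unadjusted two-sided 5% paired t test with 11 df then has power 87.5% at SD 0.8, 80.0% at 0.89, 79.1% at 0.9 and 70.4% at 1.0, so the statement reproduces. At SD 0.9, power is 60% at 0.05/3 and 47% at 0.05/6. The plan, however, calls this SD the SD of the difference; on that reading unadjusted power at 0.9 is 42%.

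The error was found by simulation (400,000 replicates per cell): F test at 5%, then two-sided 5% t tests on all six pairs, counting trials in which the gate opens and at least one truly null pair is significant. Ranges cover SD 0.8 to 1.0, both readings of the SD, and 30 or 21 df.

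| True pattern | Effect 0.5 | Effect 0.25 |
|---|---|---|
| No modality works | 5.0% | 5.0% |
| Exactly one works | 9.0% to 11.9% | about 5.5% to 9% |
| All three work equally | 9.1% to 11.8% | about 5.5% to 9% |
| Two work equally | 8.2% to 9.7% | 5.3% to 8.3% |

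(In the first row the effect is zero, so the columns coincide.) With graded effects of 0.5, 0.25 and 0.25 the figure is 3.5% to 4.9%. Replacing the t value by the three-group Tukey value behind the same gate (Fisher-Hayter; 2.465 at 30 df) gives, at effect 0.5, 4.6% to 5.0% when one or all three work and 3.7% to 4.0% when two work equally; it gives 4.8% to 4.9% when none works.

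These rates need one value per subject-night. If four daytime bouts entered a model with only a subject intercept, and 10% to 20% of the residual variance were shared within a subject-night (both assumed), the gate itself would reject in about 12% to 20% when no modality works.

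**The case against.** The established defect in the second point is that the method is not named. A reader might infer from the FDR sentence, or from the match with the stated power, that the primary pairs are unadjusted and that the trial carries a 9% to 12% error. The documents do not support that. They are silent on the method, a power calculation for one contrast does not fix the post-hoc procedure, and the match needs the plan's SD re-read as a single-measurement SD. They also do not say whether the FDR adjustment runs over outcomes, over modality pairs or both. If over outcomes, a single primary measure lacks nothing comparable.

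The inflation also depends on exact ties and is moderate for single claims. When one modality works at effect 0.5, a false stim-versus-sham difference occurs in 7.0% to 8.9% and a false benefit in 3.5% to 4.5%. A false best modality, beating both others, stays at or below about 5%. These objections stand and make this the lesser point.

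On Hypothesis 5, the 7%, 41% and 65% rest wholly on assumed SDs, and a margin can be rescaled if the data are standardized. Both are fair. A reader might also infer that the plan would declare safety from a non-significant F test; it does not say so. What remains is that no described analysis compares anything with the margin, whatever the SD or scale.

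**Conclusion.** The main point holds without any numerical assumption: Hypothesis 5 states a margin, and the analysis section contains no test or confidence limit that uses it. The size of the risk if a non-significant F test were used instead (about 7% to 65%) depends on an assumed lapse-difference SD of 2 to 4.

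The secondary point holds conditionally. No alpha or adjustment is stated for the daytime PVT-B pairs. If they are two-sided 5% tests, with normal errors and one value per subject-night, the chance of any false pair is about 9% to 12% at the plan's own effect of 0.5, and 5.5% to 9% at 0.25, when exactly one modality works or all three work equally. It is 5% when none works, and there is no excess in the graded pattern examined. With repeated daytime bouts and only a subject intercept, even the 5% would not hold. Both matters should be corrected; neither shows that a reported result is wrong.

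**What to change.** **Emergent awakening.** Whatever the F test shows, report for each modality the model-based stim-minus-sham difference in raw lapses and compare its upper one-sided 97.5% confidence limit with 2. If the claim is that all three modalities together are non-inferior, no adjustment is needed. If claims are made per modality, use one-sided Dunnett limits. Their cost, at a true difference of 0, is the drop in power from 92% / 61% / 39% to 83% / 45% / 25% at the assumed SDs of 2 / 3 / 4.

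**Daytime.** State alpha, keep the gate, and use the Fisher-Hayter critical value for the six modality pairs. Apply it to one daytime value per subject-night, for example the mean over bouts, or add a subject-by-night random effect. For one working modality against sham at effect 0.5 and 30 df, power falls from 88% to 81% at single-measurement SD 0.8 and from 78% to 70% at 0.9. If those SDs are of the difference, it falls from 44% to 36% and from 34% to 27%.

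Both changes need only SAP wording and a few lines of SAS code, and no new data. The section is written largely in the past tense; if the data have already been analysed, report both analyses as not pre-specified.

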### **Sleep Inertia Test Bout**

The Sleep Inertia Test Bout was administered at the time of emergent awakenings, and consisted of two measures that were developed and validated to be sensitive to sleep inertia: the Brief Psychomotor Vigilance Test (PVT-B) to assess behavioral alertness and psychomotor speed (Basner et al., 2011); and the Digit Symbol Substitution Test (DSST) to assess cognitive processing throughput. In addition, we administered the Descending Subtraction Task (DST), a validated measure of working memory sensitive the effects of sleep loss and sleep inertia (Dinges, 1990; Dinges et al., 1985), as well as Visual Analog Scales (VAS) to assess subjective ratings of mental fatigue, tiredness, physical exhaustion, level of stress, sleep quality, and sleepiness.

The PVT-B is a well-validated test based on vigilant attention and reaction time (Basner & Dinges, 2011; Lim & Dinges, 2008). Subjects are instructed to monitor a rectangular box on the screen and press the space bar as quickly as possible each time a millisecond counter appears. Each PVT-B reaction time is displayed for one second as feedback. Subjects are asked to respond as quickly as possible without committing false starts in the absence of stimuli.

The 1.5-minute Digit Symbol Substitution Test (DSST) is validated to be sensitive to fatigue from sleep loss (Van Dongen et al., 2003; Dinges et al., 1985). The test is based on the original version in the Wechsler Adult Intelligence Scale. Subjects are presented with a legend that pairs unique symbols to digits (1 through 9). Symbols are then sequentially presented on the screen in random order. Subjects are instructed to press the corresponding number key as soon as possible. On each test administration, the symbol and digit correspondence is randomly reassigned. The DSST measures cognitive throughput based on perception and memory.

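### The false-discovery-rate correction also covers DSST and DST scores taken at emergent awakening, so a harm on these supporting Aim 5 tests is harder to flag; the PVT-B criterion is unaffected

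*Combined protocol and SAP*

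**What the plan says.** Under Specific Aims, Aim 5 is to "Assess any potential adverse effects of SmartSleep utilization during sleep restriction, especially related to sleep inertia after emergent awakening". Its hypothesis sets one formal criterion: performance after awakening is to be "non-inferior relative to sham stimulation based on a non-inferiority margin of 2 lapses on the PVT-B". No margin is given for any other test.

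The section on the Sleep Inertia Test Bout states "The Sleep Inertia Test Bout was administered at the time of emergent awakenings" and that it "consisted of two measures that were developed and validated to be sensitive to sleep inertia", namely the PVT-B and the DSST. It then continues: "In addition, we administered the Descending Subtraction Task (DST), a validated measure of working memory sensitive the effects of sleep loss and sleep inertia". The Figure 2 caption names only the PVT-B and DSST for the bout. The Figure 3 caption shows that the DSST and DST were also given by day.

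The Statistical Approach says "The primary outcome was the number of lapses" on the PVT-B, both after emergent awakenings and during the day. It then says "Performance on the Digit Symbol Substitution (DSST), Descending Subtraction Task (DST), and spaceflight relevant task (ROBoT) were treated as secondary outcomes", without separating awakening from daytime scores, and places the remaining tests in a tertiary tier. On multiplicity it says "Statistical tests for secondary and tertiary outcomes were adjusted with the false discovery rate method". It does not say whether secondary and tertiary tests form one family, how many tests a family holds, what false-discovery rate is used, or whether the type-III tests, the post-hoc contrasts or both are adjusted.

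**The concern.** A multiplicity correction protects against false positive claims. That suits outcomes on which a benefit may be claimed. On an outcome measured to detect harm, it lowers the chance of flagging a real harm.

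The DSST and DST at the alarm serve both purposes under the plan as written. They belong with Aim 5 by content and with the efficacy outcomes by statistical tier. The protocol describes the DSST as a measure of cognitive throughput and the DST as one of working memory, so a loss confined to those functions would show on these two tests and might not show on PVT-B lapses. The only analysis described for them is a test of difference. Whether such a loss reaches significance can then depend on how unrelated daytime, spatial and operational tests turned out.

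**Working it through.** **Inputs from the plan:** 12 subjects, each receiving all four conditions; correlation between measurements 0.8; SD varied from 0.8 to 1; effect 0.5; power above 80% for SD below 0.9.

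**Assumptions, because the plan is silent:** two-sided alpha 0.05; Benjamini-Hochberg with q = 0.05; independent tests; one paired contrast (modality minus sham) per outcome, leaving out the preceding type-III test.

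**Step 1. Reproduce the plan's power.** Take the SD as that of a single measurement.

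- SD of the difference = 0.9 × √(2 × (1 − 0.8)) = 0.569
- Standardised difference = 0.5 / 0.569 = 0.878
- Noncentrality = 0.878 × √12 = 3.04, with 11 degrees of freedom
- Power = 79.1%. At SD 0.85 it is 83.4%, and at SD 0.8 it is 87.5%.

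This agrees with the plan's statement to within about one point. The plan's wording, however, calls the quantity the SD of the difference. Read that way, SD 0.9 gives 42.0% before any correction. The rest uses the reading that reproduces the plan.

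**Step 2. Direction.** With p-values in ascending order, the Benjamini-Hochberg adjusted value at rank i is the minimum over j ≥ i of (m / j) × p(j). Since m / j ≥ 1 and p(j) ≥ p(i), it cannot be below the raw value. A raw p of 0.03 that is the smallest in its family, with the others large, becomes up to 3 × 0.03 = 0.09, 5 × 0.03 = 0.15, or 1 (34 × 0.03, capped) in families of 3, 5 and 34.

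**Step 3. Family sizes.**

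- 3: DSST, DST and ROBoT, as listed.
- 5: DSST and DST each split into awakening and daytime, plus ROBoT.
- 34: those 5, plus 20 Cognition scores (10 tests × accuracy and speed), 7 spatial tasks, 6DF and Lunar Lander: 5 + 20 + 7 + 2. This is an assumed upper case.

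**Step 4. Power per harmed test after correction** (SD 0.9; 8,000 simulated trials per row, Monte Carlo standard error at most √(0.25 / 8000) = 0.6 points; unadjusted about 79% throughout):

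| Family | True effects in the family | Power | Loss, points |
|---|---|---|---|
| 3 | 1 | 61% | 18 |
| 3 | 2 | 70% | 9 |
| 3 | 3 | 76% | 3 |
| 5 | 2 | 60% | 19 |
| 5 | 5 | 75% | 4 |
| 34 | 1 | 22% | 57 |
| 34 | 2 | 25% | 54 |
| 34 | 10 | 46% | 33 |
| 34 | 34 | 74% | 5 |

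As a cross-check, exact power at the strictest Benjamini-Hochberg threshold, 0.05 / m, is 60% (m = 3), 51% (m = 5) and 21% (m = 34). The loss is therefore roughly 3 to 58 points. It is small when most of the family truly differs and large when it does not.

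**The case against.** The strongest reply is that the Aim 5 decision does not rest on these tests. Hypothesis 5 is framed on PVT-B lapses, which are primary and outside the correction. This stands, and it limits the point to supporting evidence. A reader might infer that the correction tilts the trial towards declaring the device safe. The documents do not support that: nowhere do they say that a non-significant DSST or DST result counts as absence of harm.

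A reader might also infer that every further efficacy test raises the bar. Under Benjamini-Hochberg this is false. With p = 0.03 and four large p-values the adjusted value is 5 × 0.03 = 0.15; adding a sixth test at p = 0.001 lowers it to 6 × 0.03 / 2 = 0.09. Only tests without small p-values raise it. Since Hypothesis 2 expects daytime benefit, the rows with few true effects are the unfavourable end.

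Other parts also stand. The DST is described as an addition to the two-measure bout and is absent from the Figure 2 caption, so its place at the alarm is less settled than the DSST's. The family of 34 is a construction: Digit Symbol Substitution is itself a Cognition test, and some spatial tasks may have been given only once. On the literal reading of the SD, low power precedes any correction. Adjusting p-values does not prevent unadjusted intervals from being reported. If the two tests had non-inferiority margins, the correction would make safety harder to claim, not easier, but no such margins are given.

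None of this supplies an exemption for the awakening scores or reverses the direction for a test of difference.

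**Conclusion.** The point holds, is of modest weight, and is confined to the supporting tests. As written, DSST and DST scores at emergent awakening fall under a correction that can only make a harm on them harder to flag. The direction is certain for a test of difference. The size depends on a family the plan does not define and on how many other outcomes in it truly differ. The power figures also rest on the assumed alpha, q, procedure, independence and per-measurement SD, and on DST having been taken at the alarm. The more defensible families are 3 and 5, where the loss is about 3 to 19 points for the combinations simulated (up to 28 for a lone effect in a family of 5, 79 − 51). The losses above 50 points need secondary and tertiary tests pooled into one family with almost no other true effects. The plan leaves that open but does not state it.

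**What to change.** In the Statistical Approach:

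- List DSST and DST at emergent awakening as supporting Aim 5 safety outcomes, outside the false-discovery-rate family.
- Report each modality-minus-sham difference with an unadjusted 95% confidence interval beside the PVT-B result.
- State that a non-significant difference on these tests is not evidence of no harm. Intervals without a margin show what size of harm remains compatible with the data; they do not establish safety.
- Keep the correction for the daytime secondary outcomes and the tertiary outcomes, and define the family and q.

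The cost is wording and a small table, with no new data. The downside is more false alarms: two tests × three modalities gives six contrasts, so if nothing differs about 6 × 0.05 = 0.3 intervals would exclude zero by chance, half of them (0.15) in the direction of harm. That is a tolerable error for a safety aim.

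The section is written largely in the past tense. If results are already known, disclose the change as post hoc and show the adjusted values alongside.

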## STUDY DESIGN

The study was conducted at the University of Pennsylvania. This placebo-controlled, double-blind, cross-over laboratory study of SmartSleep stimulations included sleep restriction to 5h time in bed for sleep on 4 consecutive nights, preceded by an 8h sleep adaptation night, and followed by a 10h recovery night (Figure 2).

The proposed sample was a total of 12 subjects to be recruited and screened for their ability to engage in the protocol and their similarities to astronauts (e.g., age 30-55y, educational background, healthy, etc.). The protocol involved monitoring of sleep-wake behaviors by actigraphy and sleep diary 2 weeks prior to and 1 week following the 7-day laboratory protocol. Participants were required to remain in the laboratory for the entire 7- day and 6-night protocol for cognitive testing at alarm awakening from sleep (sleep inertia test battery) and throughout each 19h waking period (full Cognition test battery every 4 hours). In addition, participants completed a spatial cognition battery and three tasks with operational relevance to spaceflight (Six Degrees of Freedom, ROBoT, and the Lunar Lander Simulator) once a day. The 6 laboratory nights consisted of a baseline night (8h time in bed [TIB]), 4 nights of 5h TIB (each with one of the four SmartSleep stimulus conditions), and a recovery night of 10h TIB at the end. Each of the 12 subjects received one of the SmartSleep stimulus conditions (Continuous Fixed Interval, Block,

In-Phase Adjustable, and Sham) on one of the 4 sleep restriction nights, according to a balanced orthogonal Latin Square design. This was a fully within-subjects design with high statistical power for the given sample size. This allowed us to investigate how the methodology works across the build-up of chronic sleep restriction (Figure 2).

Subjects	1	2	3	4	5	6	7	8	9	10	11	12
Lab Day 1	Familiarization testing: Cognition performance testing and operational simulation testing											
Night 1 (8h TIB)	Adaptation to SmartSleep cap: sham stim recording nocturnal sleep EEG with no emergent awakening											
Lab Day 2	Cognition performance testing and operational simulation testing											
Night 2 (5h TIB)	Sham	Stim 1	Stim 2	Stim 3	Sham	Stim 1	Stim 2	Stim 3	Sham	Stim 1	Stim 2	Stim 3
	Emergent Awakening (Sleep Inertia Test Bout)											
Lab Day 3	Cognition performance testing and operational simulation testing											

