The Cognition battery (Basner et al., 2015; Moore et al., 2017) was administered on calibrated laptop computers. On average, 5 ISS astronauts required only 16.5 min to answer a brief survey followed by their performance on the 10 Cognition tests. We have generated software that automatically extracts key Cognition accuracy and speed outcomes. Facilitating our large database of Cognition tests, we determined loading and difficulty of individual stimuli via Item Response Theory (Embretson and Reise, 2000), which increases the power for our analyses relative to analyses based on standard accuracy outcomes (e.g., percent correct). The data analysis process was as follows: (1) extract one key accuracy and speed outcome for each test; (2) correct outcomes for practice and stimulus set difficulty effects; and (3) standardize outcomes based on baseline performance of all subjects (we will also generate speed, accuracy, and efficiency scores across cognitive domains).

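### The stated power above 80% is reproduced only with a single-measurement SD, and then it applies to an effect above about 0.54 to 0.56 SD; for a true 0.5 SD effect it is about 70% to 74%

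*Combined protocol and SAP*

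**What the plan says.** The power statement is in the last paragraph of Statistical Approach, with Figure 4 (not available to this review). Its inputs and result are:

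- Correlation: "we assumed a correlation between measurements of 0.8".
- Spread: the authors "varied the standard deviation of the difference between modalities/sleep restriction nights from 0.8 to 1".
- Result: "We expect to have >80% power to find a medium effect size of 0.5 statistically significantly different for standard deviations <0.9".

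The paragraph gives no alpha level, no sidedness and no source for the SD range. The sample size is in Study Design ("The proposed sample was a total of 12 subjects to be recruited"), and the comparison is within subject: "Each subject was exposed to all 4 modalities (within-subject study design").

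Two sentences bear on the measurement scale. Statistical Approach says "Cognitive test data were standardized to baseline performance". The Cognition Test Battery section, describing how that battery is processed, says the team will "standardize outcomes based on baseline performance of all subjects".

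**The concern.** Two things in the power paragraph do not fit together.

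First, a correlation between measurements is needed only to turn the SD of one measurement into the SD of a paired difference. If the SD supplied is already that of the difference, the 0.8 has no role. So either the label or the use of the correlation is wrong.

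Second, a medium effect size of 0.5 is a standardized quantity. If the effect is 0.5 SD, paired power depends only on the sample size and the correlation, and cannot improve as the SD falls. The plan's power does depend on the SD, so its 0.5 must be a fixed difference in measurement units.

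This is the only power statement in the documents, and Study Design describes the within-subject design as highly powered for its size. A reader who takes it at face value would treat a null result as strong evidence against an effect of 0.5 SD.

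**Working it through.** **Inputs.** n = 12 (Study Design); correlation r = 0.8, difference 0.5 and SD from 0.8 to 1 (Statistical Approach). Two-sided alpha of 0.05 is my assumption.

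**Method.** Noncentral t power for a comparison of two conditions, with noncentrality λ = 0.5 × √12 / SD_diff = 1.732 / SD_diff. Two error df are used:

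- 11 df: paired t-test, 12 − 1.
- 21 df: planned model with modality, night, their interaction and subject. There are 48 observations and 1 + 3 + 3 + 9 + 11 = 27 parameters, leaving 21. For the layout in Figure 2 the standard error of a modality contrast equals the paired one, so only the df change.

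**Step 1: the label as printed (SD_diff = SD).**

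| SD of difference | λ | Power, 11 df |
|---|---|---|
| 0.8 | 2.17 | 50.6% |
| 0.9 | 1.92 | 42.0% |
| 1.0 | 1.73 | 35.3% |

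Power does not approach 80% anywhere in the plan's range.

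**Step 2: reproducing the plan's figure (SD of one measurement).** Here SD_diff = SD × √(2 × (1 − 0.8)) = 0.632 × SD.

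| Single-measurement SD | SD_diff | λ | Power, 11 df | Power, 21 df | 0.5 in SD units |
|---|---|---|---|---|---|
| 0.8 | 0.506 | 3.42 | 87.5% | 90.4% | 0.625 |
| 0.9 | 0.569 | 3.04 | 79.1% | 82.7% | 0.556 |
| 1.0 | 0.632 | 2.74 | 70.4% | 74.3% | 0.500 |

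Power of 80% is reached at SD 0.89 (11 df) or 0.93 (21 df). The paired t-test therefore reproduces the plan's cut-off of 0.9 closely, and this reading is evidently the one used.

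**Step 3: what effect that power belongs to.** The last column is 0.5 / SD. At the 80% points it is 0.5 / 0.89 = 0.56 (11 df) and 0.5 / 0.93 = 0.54 (21 df). These are the smallest standardized effects that 12 subjects can detect with 80% power at r = 0.8.

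**Step 4: power for an effect of 0.5 SD.** If the difference is 0.5 × SD, then λ = 0.5 × √12 / 0.632 = 2.74 whatever the SD. Power is 70.4% (11 df) or 74.3% (21 df).

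**Step 5: sensitivity to sidedness.** A one-sided 5% test (11 df) would give 82.1% for a 0.5 SD effect. It would also give 88.6% at SD 0.9, which does not match the plan's cut-off, so the two-sided assumption fits better.

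**The case against.** The strongest reply is that the plan makes no arithmetic error. Its claim is conditional on SDs below 0.9, and on the single-measurement reading it is reproduced. The stated range runs up to 1, so Figure 4 may already show the lower power there. This stands: the faults are a wrong label, an effect described as something it is not, and a favourable condition without a stated basis.

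A reader might go further and infer that standardizing to baseline makes the SD 1 by construction, so that an SD below 0.9 is ruled out and the trial misses its own claim. The documents do not support that, for four reasons.

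- Standardization fixes the SD at 1 only for a single baseline test. The power input concerns the restriction nights, for which no SD is given. It could be larger: at an assumed 1.1, with the difference held at 0.5, power is 62% (11 df) to 66% (21 df). It could be smaller for averaged daytime bouts: five bouts with an assumed between-bout correlation of 0.7 give √(0.7 + 0.3/5) = 0.87, which meets the plan's condition.
- The all-subjects standardization is described for the Cognition battery, a tertiary outcome. The primary outcome is a count of PVT-B lapses, and the documents do not say outright that lapses are standardized.
- The adaptation night has no emergent awakening, so that test has no baseline of its own and its SD is not 1 by definition.
- Hypothesis 5 tests emergent awakenings for non-inferiority with a margin of 2 raw lapses. Power to detect a 0.5 SD difference does not answer that question on any reading.

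None of this affects Steps 1 to 4, which need no assumption about the true SD.

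**Conclusion.** The concern holds as a fault in the labelling and interpretation of the power statement. Taken literally, the statement gives 35% to 51% power (11 df) over its own SD range. On the only reading tried that reproduces it, power above 80% belongs to effects above about 0.54 to 0.56 SD. An effect of 0.5 SD has about 70% to 74% power, roughly 6 to 10 points below the 80% mark.

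These figures rest on n = 12 with complete data, r = 0.8 as the plan assumes, a two-sided 5% level (my assumption), and one pairwise comparison with no multiplicity adjustment. They do not show that the SD on restriction nights is 1, nor that the trial fails a claim it made at SD 1.

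**What to change.** Revise the power paragraph and the labels of Figure 4:

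1. Label the SD as that of a single measurement, and state alpha and sidedness.
2. Replace the result with wording such as: *With n = 12 and correlation 0.8, power for a 0.5 SD difference between two conditions is about 70% (paired t) to 74% (model df); the effect detectable with 80% power is 0.54 to 0.56 SD.*
3. Keep a condition of SD below 0.9 only with a stated basis, such as the number of daytime bouts averaged. In that case call 0.5 a difference in stated units, not an effect size.
4. Say whether PVT-B lapses are standardized, and if so how.
5. Do not present this figure as the power of the emergent-awakening non-inferiority test.

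The cost is one rewritten paragraph, a relabelled figure and a less favourable stated power. Conduct and sample size do not change.
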